#### **9.2.1.2 Reporting Procedures for Serious Adverse Events**

The investigator is responsible for ensuring that all serious adverse events observed by the investigator or reported by the subject that occur after signing of the informed consent through 30 days after the last day of the dosing interval of investigational product are recorded in the subject's medical record and are submitted to Amgen. All serious adverse events must be submitted to Amgen within 24 hours following the investigator's knowledge of the event via the Event eCRF.

If the electronic data capture (EDC) system is unavailable to the site staff to report the serious adverse event, the information is to be reported to Amgen via an electronic Serious Adverse Event (eSAE) Contingency Report Form within 24 hours of the investigator's knowledge of the event. See [Appendix B](#) for a sample of the Serious Adverse Event Worksheet/electronic Serious Adverse Event Contingency Report Form. For EDC studies where the first notification of a Serious Adverse Event is reported to Amgen via the eSerious Adverse Event Contingency Report Form, the data must be entered into the EDC system when the system is again available.

The investigator must assess whether the serious adverse event is possibly related to the investigational product. This relationship is indicated by a "yes" or "no" response to the question: Is there a reasonable possibility that the event may have been caused by the investigational product? Relatedness means that there are facts or reasons to support a relationship between investigational product and the event.

The investigator is expected to follow reported serious adverse events until stabilization, resolution or patient death.

New information relating to a previously reported serious adverse event must be submitted to Amgen. All new information for serious adverse events must be sent to Amgen within 24 hours following knowledge of the new information. If specifically requested, the investigator may need to provide additional follow-up information, such as discharge summaries, medical records, or extracts from the medical records.

Information provided about the serious adverse event must be consistent with that recorded on the Event eCRF.

If a subject is permanently withdrawn from protocol-required therapies because of a serious adverse event, this information must be submitted to Amgen.

To comply with worldwide reporting regulations for serious adverse events, the treatment assignment of subjects who develop serious, unexpected, and related adverse events may be unblinded by Amgen before submission to regulatory authorities.

Amgen will report serious adverse events and/or suspected unexpected serious adverse reactions as required to regulatory authorities, investigators/institutions, and IRBs/IECs in compliance with all reporting requirements according to local regulations and good clinical practice.

The investigator is to notify the appropriate IRB/IEC of serious adverse events occurring at the site and other adverse event reports received from Amgen, in accordance with local regulatory requirements and procedures.

#### **9.2.1.3 Reporting Serious Adverse Events After the Protocol-required Reporting Period**

There is no requirement to monitor study subjects for serious adverse events following the protocol-required reporting period or after end of study. However, these serious adverse events can be reported to Amgen. In some countries (eg, European Union [EU] member states), investigators are required to report serious adverse events that they become aware of after end of study. If serious adverse events are reported, the investigator is to report them to Amgen within 24 hours following the investigator's knowledge of the event.

Serious adverse events reported outside of the protocol-required reporting period will be captured within the safety database as clinical trial cases for the purposes of expedited reporting.

### **9.3 Pregnancy and Lactation Reporting**

If a female subject becomes pregnant, or a male subject fathers a child, while the subject is taking AMG 397 report the pregnancy to Amgen Global Patient Safety as specified below.

In addition to reporting any pregnancies occurring during the study, investigators should report pregnancies that occur through 3 months after the last dose of AMG 397.

The pregnancy should be reported to Amgen Global Patient Safety within 24 hours of the investigator's knowledge of the pregnancy. Report a pregnancy on the Pregnancy Notification Worksheet ([Appendix C](#)). Amgen Global Patient Safety will follow-up with the investigator regarding additional information that may be requested.

If a female subject becomes pregnant during the study, the investigator should attempt to obtain information regarding the birth outcome and health of the infant.

If the outcome of the pregnancy meets a criterion for immediate classification as a Serious Adverse Event (eg, female subject experiences a spontaneous abortion, stillbirth, or neonatal death or there is a fetal or neonatal congenital anomaly) the investigator will report the event as a Serious Adverse Event.

If a female breastfeeds while taking protocol-required therapies report the lactation case to Amgen as specified below.

In addition to reporting a lactation case during the study, investigators should report lactation cases that occur through 3 months after the last dose of protocol-required therapies.

Any lactation case should be reported to Amgen Global Patient Safety within 24 hours of the Investigator's knowledge of event. Report a lactation case on the Lactation Notification Worksheet ([Appendix C](#)). Amgen Global Patient Safety will follow-up with the investigator regarding additional information that may be requested.

If a male subject's female partner becomes pregnant, the investigator should discuss obtaining information regarding the birth outcome and health of the infant from the pregnant partner.

## **10. STATISTICAL CONSIDERATIONS**

### **10.1 Study Endpoints**

#### **Primary Endpoints:**

- Incidence of dose limiting toxicities (DLTs), treatment-emergent adverse events, treatment-related adverse events, and clinically-significant changes in vital signs, physical examinations, electrocardiogram (ECGs) and clinical laboratory tests

#### **Secondary Endpoints:**

- Efficacy parameters:
  - ORR using response criteria per the following:
    - International Myeloma Working Group (IMWG) for MM subjects
    - Lugano Classification for NHL subjects
    - Revised International Working Group (IWG) for AML subjects

- Duration of response
- Progression Free Survival (PFS) and Overall Survival (OS)
- AMG 397 PK parameters including, but not limited to, maximum observed concentration ( $C_{max}$ ), time of maximum observed concentration ( $T_{max}$ ), area under the concentration-time curve (AUC), clearance (CL) and half-life ( $t^{1/2}$ )

#### **Exploratory Endpoints:**

- AMG 397 exposure/efficacy and exposure/safety relationships
- AMG 397 metabolites in plasma and urine
- Increased expression of BAX and Caspase 3 in monocytes or blast cells and/or decrease in circulating monocyte counts
- Patient responses according to biomarkers of tumor cells including but not limited to protein levels of pro-survival family members, FISH/cytogenetic analysis, gene expression profiling, flow cytometric phenotyping and DNA sequencing
- Immune cell subset frequencies, absolute counts and MFIs in peripheral blood
- MRD status

#### **10.1.1 Analysis Sets**

The analysis of all endpoints, unless noted otherwise, will be conducted on the Safety Analysis Set defined as all subjects that are enrolled and receive at least 1 dose of AMG 397. The analysis of DLT will be restricted to DLT-evaluable subjects (see [Section 6.2.1.1.1](#)). The PK Analysis Set will contain all subjects who have received at least 1 dose of AMG 397 and have at least 1 PK sample collected. These subjects will be evaluated for PK analysis unless the number of data points required for analysis is not enough, or significant protocol deviations have affected the data, or if key dosing or sampling information is missing.

#### **10.2 Covariates and Subgroups**

The relationship between baseline covariates and safety/efficacy endpoints will be explored. Safety and efficacy endpoints will be summarized separately for each tumor type. Details regarding covariates and subgroups and respective analyses are described in the Statistical Analysis Plan.

#### **10.3 Sample Size Considerations**

Up to 90 subjects will be enrolled in the study. Up to 60 subjects will be enrolled during dose escalation (up to 30 in both Group 1A and 1B). Up to 30 subjects will be enrolled into the dose expansion part (up to 10 in each Group 2A, 2B & 2C).

The sample sizes are based on practical considerations and it is consistent with conventional oncology studies with the objective to identify the MTD. During

dose-escalation and with 3 subjects in a cohort, there is a 27 to 70% probability of observing at least one DLT if the true DLT rate is 10 to 33%. With 10 subjects respectively in in dose expansion group, there is a 40% to 65% probability of observing at least 1 adverse event if the true event rate is 5% to 10%. Exact 80% binomial CI will be provided for ORR. With the 10 subjects in each dose expansion group and a 20% ORR, the 80% CI would be 5% to 45%.

#### 10.4 Adaptive Design

A 2-parameter Bayesian Logistic Regression Model (BLRM) is used to guide dose escalation. The MTD target Toxicity Probability Interval (TPI) for DLT is (0.20, 0.33] and TPIs of (0.33, 0.60] and (0.60, 1.00] are defined as excessive and unacceptable, respectively. The design seeks to identify a dose most likely to have a DLT rate in the target TPI, but with overdose control that limits the possibility the dose has an excessive or unacceptable DLT rate (Babb et al, 1998). The overdose control limit is defined as less than a 0.40 probability of an excessive or unacceptable TPI. Based on accumulating safety data, the DLRT may implement an overdose control limit of less than a 0.25 probability of an excessive or unacceptable TPI. The probability of a DLT at dose level  $d_i$  is assumed to follow a Bernoulli distribution with probability  $p_i$  where the logit of  $p_i$  increases linearly with the log of the standardized dose in the following 2-parameter logistic model:

$$\log [p_i / (1-p_i)] = \text{logit}(p_i) = \log[a] + \exp(\log[b]) \log (d_i / d_{\text{ref}})$$

where  $a$  and  $b$  are random variables and  $d_{\text{ref}}$  is 1 of the planned dose selected as the reference dose.

A bi-variate normal prior distribution (Neuenschwander et al, 2008) is used for  $\theta = (\log a, \log b)$  where the probability that the true DLT rate is  $\leq 0.40$  at the lowest planned dose of 80 mg is 0.90 and the probability the true DLT rate is  $\leq 0.05$  at the reference dose of 640 mg is 0.05. These values are selected such that  $p_i$  is 0.05 for the starting dose and 0.25 for the reference dose. Model sensitivity to the prior will also be investigated and in particular the BLRM will be examined using a prior having a lower reference dose (eg, 320 mg). Operating characteristics for this BLRM design are described in [Appendix D](#).

During dose expansion, Amgen will conduct evaluations of the ongoing grade 4 or higher adverse event rate to assess if the threshold for early trial termination has been reached. The stopping rules use a Bayesian approach proposed by [Thall, et al \(1995\)](#) to terminate

the study if the posterior probability that the grade 4 or higher adverse event rate is greater than 20% is  $> 90\%$ . The stopping boundaries assuming a prior distribution of Beta (0.40, 1.60) are presented in Table 10 and the operating characteristics with pre-specified batch size of 10 new subjects per batch are presented in Table 2. Subjects including in a batch may come from different tumor types. The evaluations could occur more frequently if necessary to address emerging safety concerns. The operating characteristics in Table 11 provide the probability of stopping the study early for given hypothetical true rate of grade 4 or higher adverse events, whereas the stopping criteria in Table 10 are based on situations where the empirical evidence would result in a posterior probability of  $\geq 90\%$  that the true grade 4 or higher adverse event rate is  $\geq 20\%$ .

**Table 10. Stopping Boundary for Dose Expansion With Posterior Probability of 90% and Grade 4 or Higher Adverse Event Limit of 20%**

Number of subjects	Stop study if observing these many grade 4 or higher adverse events
10	$\geq 5$
20	$\geq 7$
30	Study Complete

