## **9. SAFETY DATA COLLECTION, RECORDING, AND REPORTING**

### **9.1 Definition of Safety Events**

#### **9.1.1 Adverse Events**

An adverse event is defined as any untoward medical occurrence in a clinical trial subject. The event does not necessarily have a causal relationship with study treatment. The investigator is responsible for ensuring that any adverse events observed by the investigator or reported by the subject are recorded in the subject's medical record.

The definition of adverse events includes worsening of a pre-existing medical condition. Worsening indicates that the pre-existing medical condition or underlying disease (eg, diabetes, migraine headaches, gout) has increased in severity, frequency, and/or duration more than would be expected and/or has an association with a significantly worse outcome than expected. A pre-existing condition that has not worsened more than anticipated (ie, more than usual fluctuation of disease) during the study, or involves

an intervention such as elective cosmetic surgery or a medical procedure while on study, is not considered an adverse event.

Record a single event for each increased level of severity on the Event eCRF.

For situations when an adverse event or serious adverse event is due to Multiple Myeloma or Non-Hodgkin's Lymphoma report all known signs and symptoms. Death due to disease progression in the absence of signs and symptoms should be reported as the primary tumor type (eg, multiple myeloma).

**Note:** The term "disease progression" should not be used to describe the adverse event.

The investigator's clinical judgment is used to determine whether a subject is to be removed from treatment due to an adverse event. In the event a subject, or subject's legally acceptable representative requests to withdraw from protocol-required therapies or the study due to an adverse event, refer to [Section 8.1](#) for additional instructions on the procedures recommended for safe withdrawal from protocol-required therapies or the study.

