**Table 11. Operating Characteristics With Batch Size of 10 Subjects**

True grade 4 or higher adverse event rate	Probability of early stopping of dose expansion	Average dose expansion sample size
0.10	0.4%	29.9
0.15	2.7%	29.6
0.20	9.7%	28.7
0.25	22.9%	26.9
0.30	40.8%	24.4

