Abbreviation or Term	Definition/Explanation
PFS	Progression free survival
PR	PR interval is measured from the beginning of the P wave to the beginning of the QRS complex in the heart's electrical cycle as measured by ECG or partial response
PK	Pharmacokinetic
QRS	QRS interval is the interval between the Q wave and the S wave in the heart's electrical cycle as measured by ECG; represents the time it takes for the depolarization of the ventricles
QT	QT interval is a measure of the time between the start of the Q wave and the end of the T wave in the heart's electrical cycle as measured by ECG
QTc	QT interval corrected for heart rate using accepted methodology
QTcF	QT interval corrected for heart rate using Fridericia's formula
RP2D	Recommended phase 2 dose
RR	Relapsed or Refractory
$t_{1/2}$	Half-life
t_{max}	Time of maximum observed serum concentration
TPI	Toxicity probability interval
TTR	Time to response
WHO	World health organization

1. Introduction

The purpose of this Statistical Analysis Plan (SAP) is to provide details of the statistical analyses that have been outlined within the protocol amendment 4 for Study 20170173 - AMG 397 dated 09 December 2020. The scope of this plan includes the interim analysis, the primary analysis and the final analysis that are planned and will be executed by the Amgen Global Bio-statistical Science department unless otherwise specified.

2. Objectives, Endpoints and Hypotheses

- **Indications:** Relapsed or Refractory (RR) Multiple Myeloma (MM), Non-Hodgkin's Lymphoma (NHL), Myelodysplastic Syndrome (MDS) or Acute Myeloid Leukemia (AML).

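### The expansion stopping table counts grade 4 or higher adverse events, but its boundaries and operating characteristics hold only for subjects with at least one such event

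*Protocol*

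**What the plan says.** Protocol Section 10.4 monitors the dose expansion in batches of 10 subjects. The study is to end once the "posterior probability that the grade 4 or higher adverse event rate is greater than 20"% exceeds 90%, under a Beta(0.40, 1.60) prior.

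Table 10 gives the boundary. Its title is "Stopping Boundary for Dose Expansion With Posterior Probability of 90% and Grade 4 or Higher Adverse Event Limit of 20"%, its first column is a number of subjects, and its second column is headed "Stop study if observing these many grade 4 or higher adverse events": 5 or more at 10 subjects, 7 or more at 20.

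The text links the table to the rule: "the stopping criteria in Table 10 are based on situations where the empirical evidence would result in a posterior probability of" at least 90%. Table 11 then gives stopping probabilities and average sample sizes by "True grade 4 or higher adverse event rate".

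Two other places bear on the unit. Section 10.3 says of an expansion group of ten: "there is a 40% to 65% probability of observing at least 1 adverse event if the true event rate is 5% to 10"%. Section 9.1.1, on recording, says: "Record a single event for each increased level of severity on the Event eCRF".

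**The concern.** A posterior probability under a Beta prior concerns a proportion, with subjects as the denominator. The instruction in the Table 10 header is a count of events. The two agree only if no subject has more than one grade 4 or higher event, and nothing in Section 10.4 says that a subject counts once.

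The rule covers any grade 4 or higher adverse event in relapsed or refractory myeloma, DLBCL and AML, so two different qualifying events in one subject are plausible. The recording rule in Section 9.1.1 adds little: it creates a second qualifying record only when a toxicity moves from grade 4 to grade 5.

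Table 10 is what a team would look up when deciding whether to end the expansion. Followed as printed, it can end the expansion when the protocol's own 90% criterion is not met, and Table 11 would not describe how the rule behaves.

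**Working it through.** **Inputs (Protocol 10.4).** Prior Beta(0.40, 1.60); limit 20%; threshold 90%; looks at 10 and 20 subjects; complete at 30.

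**1. Boundaries, each subject counted once.** With r affected subjects among n, the posterior is Beta(0.4 + r, 1.6 + n − r). The criterion is P(p > 0.20) > 0.90.

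| n | r | P(p > 0.20) |
|---|---|---|
| 10 | 3 | 0.720 |
| 10 | 4 | 0.895 |
| 10 | 5 | 0.971 |
| 20 | 5 | 0.666 |
| 20 | 6 | 0.826 |
| 20 | 7 | 0.9235 |

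The smallest r above 0.90 is 5 at n = 10 and 7 at n = 20, as in Table 10.

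**2. Table 11, each subject counted once.** With X and Y independent Bin(10, p):

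- S1 = P(X ≥ 5)
- S2 = Σ over x = 0 to 4 of P(X = x) · P(Y ≥ 7 − x)
- Stopping probability = S1 + S2
- Average size = 10·S1 + 20·S2 + 30·(1 − S1 − S2)

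At p = 0.20: S1 = 0.0328 and S2 = 0.0644, so stopping is 0.0972. The average size is 0.328 + 1.288 + 27.084 = 28.70.

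| True rate | Stop, computed | Stop, Table 11 | Average N, computed | Average N, Table 11 |
|---|---|---|---|---|
| 0.10 | 0.35% | 0.4% | 29.948 | 29.9 |
| 0.15 | 2.68% | 2.7% | 29.63 | 29.6 |
| 0.20 | 9.72% | 9.7% | 28.70 | 28.7 |
| 0.25 | 22.94% | 22.9% | 26.92 | 26.9 |
| 0.30 | 40.84% | 40.8% | 24.41 | 24.4 |

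All five rows match. As a contrast, Poisson event counts with mean events per subject equal to the stated rate give 0.7%, 4.2%, 12.7%, 25.9% and 41.6%, which do not match. The tables were therefore computed for subjects.

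**3. Section 10.3.** 1 − 0.95^10 = 0.401 and 1 − 0.90^10 = 0.651. The 40% to 65% there is also a per-subject calculation.

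**4. Header against rule on the same data.** Five events in 3 of 10 subjects meet the header, but the posterior is 0.72. Seven events in 5 of 20 subjects meet it, but the posterior is 0.67.

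**5. Size if events are counted.** The documents give no events per affected subject. Assume that a share q of affected subjects have two qualifying events and none has more. Each subject then contributes 0, 1 or 2 events with probabilities 1 − p, p(1 − q) and pq. The total over each batch of 10 is obtained by exact convolution, with the same limits of 5 and 7. The unmet-criterion columns give the chance that the header stops the study at a look where the number of affected subjects is still below the boundary.

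| q | Stop, p = 0.10 | Average N, p = 0.10 | Criterion unmet, p = 0.10 | Stop, p = 0.20 | Average N, p = 0.20 | Criterion unmet, p = 0.20 |
|---|---|---|---|---|---|---|
| 0 (Table 11 basis) | 0.35% | 29.948 | 0 | 9.72% | 28.70 | 0 |
| 0.05 | 0.82% | 29.88 | 0.48% | 13.42% | 28.15 | 4.24% |
| 0.10 | 1.38% | 29.79 | 1.06% | 17.09% | 27.60 | 8.41% |
| 0.25 | 3.57% | 29.46 | 3.28% | 27.73% | 25.98 | 20.32% |
| 0.50 | 8.24% | 28.77 | 7.99% | 43.46% | 23.49 | 37.61% |

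A simulation of 400,000 trials agrees with the stopping figures to within 0.1 percentage points.

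**The case against.** The strongest reply is that the intended unit can be inferred. The governing rule is the posterior criterion, and the text derives Table 10 from it. The table's first column counts subjects, and a Beta prior applies to a proportion. The documents also use similar shorthand elsewhere: Appendix D sets a number of DLTs beside a proportion of DLTs, and SAP Table 1 sets a number of DLTs against evaluable subjects. On this view, a team that stopped on five events in three subjects would be misapplying the rule.

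That settles what was meant, not what the table tells the team to do. The protocol's adverse event analysis (Section 10.6.2) says subject incidence when it means subjects; the Table 10 header does not.

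Other points stand as limits on the finding:

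- The error runs one way. The event count is never below the subject count, so the header can stop too early but cannot miss toxicity.
- The size depends wholly on an assumed multiplicity, and at the low end it is small.
- The unmet-criterion figures include trials that the subject-based rule would have stopped at the later look. The net rise in stopping at a 20% rate is 3.7, 7.4, 18.0 and 33.7 percentage points (13.42, 17.09, 27.73 and 43.46, each less 9.72).
- The available SAP is written for "protocol amendment 4 for Study 20170173 - AMG 397 dated 09 December 2020". Its Section 3.1 describes a redesigned study, and it does not carry this rule. Whether a later amendment reworded or dropped the rule cannot be seen. Neither possibility makes the header in this protocol correct.

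**Conclusion.** The concern holds. Table 10 states a study-stopping threshold in the wrong unit: the numbers are right for subjects with at least one grade 4 or higher event, and the header asks for events. That the tables are built on subjects is shown by exact reproduction of both boundaries and all five Table 11 rows, and needs no assumption.

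The consequence does need one. If between 5% and 50% of affected subjects have two qualifying events, following the header raises the stopping probability at a true 20% rate from 9.7% to between 13% and 43%, and at a true 10% rate from 0.4% to between 0.8% and 8.2%. The cost is an expansion of at most 30 subjects ended without the stated evidence, or a dispute over the count at a look. It is not added risk to subjects.

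**What to change.** Change the second column header of Table 10 to: *Stop study if observing this many subjects with at least one grade 4 or higher adverse event*. In the Section 10.4 text and the first column of Table 11, define the rate as the proportion of subjects with at least one grade 4 or higher adverse event.

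This costs wording only. The boundaries, the prior, the 20% limit, the 90% threshold and every Table 11 figure stay as they are, and nothing has to be recalculated. If a later amendment still carries the rule, the same wording should go there.
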